7.1.2 Visit 2: 30-Month Long-Term Follow-Up

The 30-month long-term follow up is considered from the completion of 8-weeks of treatment.

1. **Record AE**
2. **Concomitant and Prior Ocular and Systemic Medications:** The Investigator will conduct a retrospective chart review and patient interview to review all medications since the previous visit.
3. **IDEEL**
4. **EQ-5D-5L**
5. **Ophthalmic Examinations:**
 - a. **BCDVA**
 - b. **External Ocular Examination**
 - c. **SLE**
 - d. **Corneal Photo without Fluorescein**
 - e. **Instill Fluorescein**
 - f. **TFBUT**
 - g. **Corneal Photography with Fluorescein**
 - h. **Corneal Sensitivity**
 - i. **Schirmer Test without Anesthesia (Schirmer I)** CCI [REDACTED]
CCI [REDACTED]

C CCI
C CCI

[REDACTED]

6. Patient Discharged from Study

7.2 EARLY WITHDRAWAL FROM STUDY

A premature discontinuation will occur when a patient who signed the ICF ceases study participation, regardless of circumstances, before the completion of the protocol procedures. Patients can be prematurely discontinued from the study for one of the following reasons:

- Withdrawal of consent
- Lost to follow-up (every effort must be made to contact the patient; a registered letter must be sent)
- Study terminated by the Sponsor
- Other reasons, such as administrative reasons
- Severe protocol violations. Before removal, these cases should first be discussed with Dompé.

The reasons for premature discontinuation will be reflected on the Study Termination Record of the CRF. For patients who prematurely discontinue, visit 2 procedures will be completed if allowed by the patient, and these patients will be considered off study and will no longer be followed.

Replacement Procedures

Patient replacement will not occur in this study.

7.3 END OF STUDY

For this study, the End of Study is defined as the date of the Last Visit of the Last Patient.

8 ENDPOINTS

8.1 STUDY ENDPOINTS

- Percentage of patients who have corneal epithelial healing at 24 months and 30 months of the long-term follow-up.
 - Percentage of patients who had corneal epithelial healing at week-8 in the DEFENDO Study, who maintain healing at month 24 and month 30 of the long-term follow-up.
 - Percentage of patients who did not have corneal epithelial healing at week-8 in the DEFENDO Study who have a healed corneal epithelium at month 24 and month 30 of the long-term follow-up.
- Percentage of patients who achieved an improvement in corneal sensitivity at 24 months and 30 months of the long-term follow-up.
 - Percentage of patients who achieved an improvement in corneal sensitivity at week-8 in the DEFENDO Study who still have improvement in corneal sensitivity at 24 months and 30 months of the long-term follow-up.
 - Percentage of patients who did not achieve an improvement in corneal sensitivity in the DEFENDO Study who have improvement in corneal sensitivity at 24 months and 30 months of the long-term follow-up.
- Change from the Baseline Visit in the DEFENDO Study in Schirmer I scores at 24 months and 30 months of the long-term follow-up.
- Change from the Baseline Visit in the DEFENDO Study in TFBUT at 24 months and 30 months of the long-term follow-up.
- Change from the Baseline Visit in the DEFENDO Study in BCDVA at 24 months and 30 months of the long-term follow-up.
- Percentage of patients who achieved a 15-letter improvement in BCDVA at 24 months and 30 months compared to the Baseline Visit and Week 8 of the DEFENDO Study.
- Change from the Baseline Visit in the DEFENDO Study in quality of life as measured with the IDEEL at 24 months and 30 months of the long-term follow-up.
- Change from the Baseline Visit in the DEFENDO Study in quality of life as measured with the EQ-5D-5L at 24 months and 30 months of the long-term follow-up.

CCI

CCI

CCI

CCI

CCI

[figure not shown]
CCI

CCI

CCI

CCI

C

8.1.3 Safety Endpoints

- AEs assessed throughout the study.
- Slit-Lamp Examination results.
- External Ocular Examination results.

9 EVALUATION OF ADVERSE EVENTS AND SAFETY INFORMATION

9.1 DEFINITIONS

Adverse Event

An **Adverse Event (AE)** is defined as any untoward medical occurrence in a patient or clinical investigation patient administered a pharmaceutical product and which does not necessarily have a causal relationship with this treatment. An AE can therefore be any unfavorable and unintended sign (including an abnormal laboratory finding), symptom, or disease temporally associated with the use of a pharmaceutical product, whether considered related to treatment. This definition includes an exacerbation of preexisting medical conditions or events, historical conditions do not present prior to study treatment in the DEFENDO Study, which reappear following study treatment, intercurrent illnesses, hypersensitivity reactions, drug-drug or drug-food interactions, medication errors, overdose (both intentional or unintentional), drug misuse/abuse, false positive laboratory test, or the significant worsening of the disease under investigation.

Adverse Drug Reaction

An **Adverse Drug Reaction (ADR)** is defined as an adverse experience, which is reasonably likely to have been caused by the drug. An adverse reaction, in contrast to an AE, is characterized by the fact that a causal relationship between a pharmaceutical product and an occurrence is suspected. Medical judgment should be used to determine the relationship, considering all relevant factors, as applicable, including pattern of reaction, temporal relationship, de-challenge or re-challenge, confounding factors such as concomitant medication, concomitant diseases, and relevant history. Adverse drug reactions may arise from use of the study treatment in the DEFENDO Study within or outside the terms of the marketing authorization or from occupational exposure. Conditions of use outside the marketing authorization include off-label use, overdose, misuse, abuse, and medication errors, occupational exposure.

The Investigator should carefully evaluate the relationship between the event and previous treatment with OXERVATE or any medicinal product administered at the AE onset. The Investigator should use the following information to help make their decision.

Arguments that may suggest a reasonable causal relationship could be:

- The event is consistent with the known pharmacology of the drug.
- The event is known to be caused by or attributed to the drug.
- A plausible time to onset of the event relative to the time of drug exposure.
- Evidence that the event is reproducible when the drug is re-introduced.
- No medically sound alternative etiologies that could explain the event (e.g., pre-existing or concomitant diseases, or co-medications).
- The event is typically drug-related and infrequent in the general population not exposed to the drug.
- An indication of dose-response (i.e., greater effect size if the dose is increased, smaller effect size if dose is diminished).

Arguments that may suggest that there is no reasonable possibility of a causal relationship could be:

- No plausible time to onset of the event relative to the time of drug exposure is evident (e.g., pre-treatment cases, diagnosis of cancer or chronic disease within days/weeks of drug administration; an allergic reaction weeks after discontinuation of the drug concerned).
- Continuation of the event despite the withdrawal of the medication, considering the pharmacological properties of the compound (e.g., after 5 half-lives). Of note, this criterion may not be applicable to events whose time course is prolonged despite removing the original trigger.
- Additional arguments amongst those stated before, like alternative explanation (e.g., situations where other drugs or underlying diseases appear to provide a more likely explanation for the observed event than the drug concerned).
- Disappearance of the event even though the study drug treatment continues or remains unchanged.

AE are to be considered related or unrelated to the study drug as described in [Section 9.3.2](#). Any AE reported in the study having a related relationship to study drug will be considered as an ADR.

Adverse Event of Special Interest (AESI)

Not applicable.

- **Serious Adverse Event**

A **Serious Adverse Event (SAE)** is defined as any untoward medical occurrence that at any dose:

- Results in death.
- Is life-threatening (i.e., the patient was at risk of death at the time of the event. It does not refer to an event which hypothetically might have caused death if it were more severe).
- Requires inpatient hospitalization or prolongation of existing hospitalization.

NOTE: In general, hospitalization means that the individual remained at the hospital or emergency ward for observation and/or treatment (usually involving an overnight stay) that would not have been appropriate in the physician's office or an out-patient setting. Complications that occur during hospitalization are AEs. If a complication prolongs hospitalization or fulfills any other serious criteria, the event is serious. When in doubt as to whether "hospitalization" occurred, the event should be considered serious.

- Results in persistent or significant disability/incapacity.

NOTE: This definition is not intended to include experiences of relatively minor medical significance such as uncomplicated headache, nausea, vomiting, diarrhea, influenza, or accidental trauma (e.g., sprained ankle), which may interfere or prevent everyday life functions, but do not constitute a substantial disruption.

- Is a congenital anomaly/birth defect.
- Is medically significant or important medical condition, i.e., an important medical event that based upon appropriate medical judgment, may jeopardize the patient, and may require medical or surgical intervention to prevent one of the outcomes listed above.

An important medical condition is an event that may not result in death, be life-threatening, or require hospitalization but may be considered a SAE when, based upon appropriate medical judgment, it may jeopardize the patient and may require medical or surgical intervention to prevent one of the outcomes listed above. Examples of such medical events include allergic bronchospasm requiring intensive treatment in an emergency room or at home, blood dyscrasias or convulsions that do not result in patient hospitalization, or the development of drug dependency or drug abuse.

Pre-planned hospitalization or hospitalization for routine treatment or monitoring of the studied indication, not associated with any deterioration in condition are not considered to be SAEs. These events must be recorded in the AE page of the CRF where a variable will be ticked to indicate that they are not SAEs.

Death shall always be reported as SAE. Cause of death shall always be specified when known.

Any preplanned surgery or procedure should be clearly documented in the site source documents by the medically qualified Investigator at the time of the patient's entry into the study. If it has not been documented at the time of the patient's entry into the study, then it should be documented as a SAE and reported to Dompé.

Dompé considers cancer and abortion (spontaneous or non-spontaneous) as SAEs, as well as any suspected transmission via a medicinal product of an infectious agent is considered a serious adverse reaction.

Unexpected Adverse Events

An AE or ADR is considered unexpected if it is not listed in the package insert of the suspected medicinal product. An event is unexpected also when it is not listed at the specificity or severity that has been observed and listed in the package insert.

The determination of expectedness shall be made based on the package insert. It is the responsibility of the Sponsor to assess whether an AE is expected or unexpected.

Suspected unexpected serious adverse reaction

A suspected unexpected serious adverse reaction (SUSAR) is defined as an adverse reaction that is both unexpected (not consistent with the applicable product information) and meets the definition of a Serious Adverse Reaction.

9.2 MONITORING FOR ADVERSE EVENTS

At each Follow Up visit, after the patient has had the opportunity to spontaneously mention any problems, the Investigator or appropriate designee should inquire about AEs by asking the standard questions:

- “Have you had any health problems since your last study visit?”
- “Have there been any changes in the medicines you take since your last study visit?”

AEs should be reported for any clinically relevant change in concomitant condition(s) that is the result of an untoward (unfavorable and unintended) change in a patient’s medical health. Anticipated day-to-day fluctuations of preexisting conditions that do not represent a clinically significant exacerbation or worsening need not be reported as AEs. Changes in any protocol-specific [ocular or] systemic parameter evaluated during the study are to be reviewed by the Investigator. In addition, the patient’s responses to any questionnaire utilized during the study are to be reviewed by the Investigator. Any untoward (unfavorable and unintended) change in a protocol-specific parameter or questionnaire response that is clinically relevant is to be reported as an AE. These clinically relevant changes will be reported regardless of causality.

9.3 RECORDING

AEs will be collected and recorded for any untoward event that occurs in a patient from the time he or she signed the ICF in the DEFENDO Study until completing the DEFENDO Long-Term Follow-up Study. Thus, any untoward medical occurrences or unfavorable and unintended signs, symptoms, or diseases that occur during the post treatment period (i.e., during the long-term follow up) should be considered AEs and/or SAEs, and consequently recorded and reported as such. Should a non-serious AE become serious, the Investigator will then follow the same reporting procedures as for SAEs.

Each AE will be described by:

- Its duration (start and stop dates)
- Severity
- Its relationship to the study drug; (related/unrelated)
- Action(s) taken
- Outcome

Medical conditions/diseases, or cancer related signs/symptoms present before starting study treatment should have been documented in the medical history section of the CRF during the DEFENDO Study; these conditions are considered AEs only if they increase either in frequency or severity during the DEFENDO Long-Term Follow-up Study.

9.3.1 Follow-Up of Patients with Adverse Events

The Investigator is responsible for adequate and safe medical care of patients during the Study and for ensuring that appropriate medical care and relevant follow-up procedures are maintained after the Study. All AEs should be followed-up to determine outcome of the reaction. The Investigator should follow up the event until resolution or stabilization of the condition. It is the Investigator's responsibility to assure that the patients experiencing AEs receive definite treatment for any AE, if required.

If the patient was hospitalized due to a SAE, a copy of the discharge summary is to be forwarded to the Sponsor as soon as it becomes available. In addition, a letter from the Investigator that summarizes the events related to the case as well as results of any relevant laboratory tests also may be requested. Further, depending upon the nature of the SAE, Dompé may request copies of applicable segments of the patient's medical records. In case of death, a copy of the autopsy report, if performed, should also be provided.

The Investigator shall inform the Sponsor with an appropriate written communication, whenever he/she becomes aware of new available information regarding the SAE once the condition is resolved or stabilized and when no more information about the event is expected. Additional information received after the initial SAE has been reported to the Sponsor should be reported as follow-up information following the same procedure and timeline as the initial SAE.

For pharmacovigilance purposes, all SAEs should be followed-up to clarify as completely as possible their nature and/or causality and until all queries have been resolved. All SAEs will be followed up until the events resolve or the events or sequelae stabilize, or it is unlikely that any additional information can be obtained after demonstration of due diligence with follow-up efforts (i.e., patient or Investigator is unable to provide additional information, or the patient is lost to follow up), unless patient has withdrawn his/her consent.

9.3.2 Relationship of AEs to a Medicinal Product

The Investigator will assess the possible relationship between the AE and the investigational medication used in the DEFENDO Study and any treatment received, including Oxervate as standard of care, in this DEFENDO Long-Term Follow-up Study, according to the criteria in the below table.

Relationship of the Adverse Event to the Medicinal Product

Unrelated	No reasonable possibility that the administration of the Medicinal Product caused the event, no temporal relationship between the Medicinal Product and event onset, or an alternate etiology has been established.
Related	It is known to occur with the Medicinal Product, is a reasonable possibility that the Study Product caused the AE, or there is a temporal relationship between the Medicinal Product and event. Reasonable possibility means that there is evidence to suggest a causal relationship between the Medicinal Product and the AE.

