7.1 STUDY VISITS AND EXAMINATIONS AND TREATMENT VISITS

7.1.1 Visit 1: 24-Month Long-Term Follow-Up

The 24-month long-term follow up is considered from the completion of 8-weeks of treatment. Site staff will conduct the following assessments in the order outlined below:

1. **Inclusion/Exclusion Criteria:** Inclusion/Exclusion criteria will be reviewed, and study eligibility will be determined.
2. **Informed Consent/Health Insurance Portability and Accountability Act (HIPAA):** Explain the purpose and nature of the study and have the patient or legally authorized representative read, sign, and date the IRB approved Informed Consent Form (ICF). Provide a photocopy of the signed document to the patient and place the original signed document in the patient's chart.
3. **Demographics, Medical and Ocular History:** These data from the DEFENDO Study will be carried forward into the current study's electronic data capture (EDC) System; thus, they do not need to be captured separately for this study.
4. **Record AE:** Record any AE since completing the DEFENDO Study in the AE eCRF. Data for AEs that have occurred since the completion of the DEFENDO Study should be obtained from retrospective chart review and / or patient interview. Additional information may be requested via medical records from all applicable healthcare providers, if necessary.
5. **Concomitant and Prior Ocular and Systemic Medications:** Record any concurrent ocular or non-ocular medications including information on all concomitant and previous medications used since completing the DEFENDO Study in the Concomitant Medications eCRF ([Section 6.2](#)). Data for topical ocular medications taken since the patient completed the DEFENDO Study should be obtained from retrospective chart review and / or patient interview. Additional information may be requested via medical records from all applicable healthcare providers, if necessary.

6. **IDEEL (Impact of Dry Eye on Everyday Life):** This questionnaire will be assessed by the patient using a self-administered format. This questionnaire is designed to assess health-related quality of life in patients with visual impairments by representing the patient perspective on the impact of vision problems on functioning.

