In addition, each IRB/IEC/Regulatory Authority and Investigator will receive appropriate periodic safety updates as per applicable local requirements and regulations.

In addition to reporting the SAE to Dompé PPD, the Investigator must also comply with the requirements related to the reporting of SAEs to the local IRB which approved the study. The requirements of IRBs vary from one IRB to another; however, as a minimum requirement, the Investigators must promptly report all suspected unexpected serious adverse reactions (SUSAR) to their IRB.

In line with provisions set forth in 21CFR312, Dompé shall notify all participating Investigators in an Investigational New Drug (IND) safety report of any suspected adverse reaction that is both serious and unexpected and of potential serious risks, from clinical studies or any other source, as soon as possible, but in no case later than:

- seven calendar days after becoming aware of the information if the event is fatal or life threatening; to be followed by any relevant information within eight days.
- fifteen calendar days after becoming aware of the information if the event is serious but neither fatal nor life threatening.

The Investigators in turn shall notify their local IRB.

Copies of all correspondence relating to reporting of any SUSARs to the local IRB should be maintained in the Investigator's Files.

Dompé shall also notify the FDA in an IND safety report of potential serious risks, from clinical studies or any other source, as soon as possible after Dompé determines that the information qualifies for reporting, shall notify of:

- Any suspected adverse reaction that is both serious and unexpected. Dompé must report an AE as a suspected adverse reaction only if there is evidence to suggest a causal relationship between the drug and the AE.
- Findings from other studies that suggest a significant risk in humans exposed to the drug. Such a finding would result in a safety-related change in the overall conduct of the clinical investigation.
- Findings from animal or in vitro testing that suggest a significant risk in humans exposed to the drug.
- Increased rate of occurrence of serious suspected adverse reactions.

When SAEs are determined to be related to treatment with other medicinal products administered during the DEFENDO Long-Term Follow-up Study, the Sponsor will also forward the report to the NDA or BLA holder, manufacturer, packer, or distributor of the marketed drug.

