Your vision may be blurred for a short time after using OXERVATE. If this happens, wait until your vision clears before you drive or use machines.

What are the possible side effects of OXERVATE?

The most common side effect of OXERVATE is eye pain, enlarged blood vessels in the white of the eyes (ocular hyperemia), swelling (inflammation) of the eye, and increase of tears (increased lacrimation).

Tell your doctor if you have any side effects that bother you. These are not all the possible side effects of OXERVATE. Call your doctor for medical advice about side effects. You may report side effects to FDA at [P](#)

P

General information about the safe and effective use of OXERVATE.

Medicines are sometimes prescribed for purposes other than those listed in a Patient Information leaflet. Do not use OXERVATE for a condition for which it was not prescribed. Do not give OXERVATE to other people, even if they have the same symptoms you have. It may harm them.

You can ask your pharmacist or doctor for information about OXERVATE that is written for health professional.

What are the ingredients in OXERVATE?

Active ingredient: cenegeamin-bkjb

Inactive ingredients: disodium hydrogen phosphate anhydrous, hydroxypropylmethylcellulose, L-methionine, mannitol, polyethylene glycol 6000, sodium dihydrogen phosphate dihydrate, trehalose dihydrate, Water for Injection, USP, and hydrochloric acid and/or sodium hydroxide to adjust pH.

Manufactured by:

Dompé farmaceutici S.p.A.
[name]
[name]
U.S. License No. 2074

Manufactured for: Dompé U.S. Inc.

PPD

For more information, go to [www.oxervate.com](#) or call **PPD**

This Patient Information has been approved by the U.S. Food and Drug Administration

Revised or Issued: October 2019

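### The Related and Unrelated definitions in Protocol 9.3.2 overlap, so one adverse event can satisfy both and be classified either way

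*Protocol*

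**What the plan says.** Protocol Section 9.3.2 applies to the DEFENDO medication and to any treatment received during follow-up, including OXERVATE given as standard of care. The investigator is to use the criteria in a two-row table.

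- **Related** has three alternatives. The first two are "It is known to occur with the Medicinal Product, is a reasonable possibility that the Study Product caused the AE"; the third is "or there is a temporal relationship between the Medicinal Product and event". A closing sentence adds: "Reasonable possibility means that there is evidence to suggest a causal relationship between the Medicinal Product and the AE".
- **Unrelated** also has three alternatives: no reasonable possibility that the product caused the event, then "no temporal relationship between the Medicinal Product and event onset, or an alternate etiology has been established".

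Section 9.1 asks for medical judgment on all relevant factors and lists arguments for and against causality, among them time to onset, known effects and alternative explanations. It then states that events are classed as related or unrelated as described in Section 9.3.2, and that "Any AE reported in the study having a related relationship to study drug will be considered as an ADR".

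Three other places supply the setting. Section 7.1.1 states: "The 24-month long-term follow up is considered from the completion of 8-weeks of treatment". Section 6.2 allows commercial OXERVATE during follow-up. Appendix 3 states: "The most common side effect of OXERVATE is eye pain, enlarged blood vessels in the white of the eyes", and goes on to name eye inflammation and increased lacrimation.

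In the SAP, Section 6.1 and Table 14.3.1.4 tabulate adverse events by closest relationship to treatment. Section 6.1 forms Related and Not Related by collapsing a five-level scale that runs from None to Highly Probable.

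**The concern.** A two-category causality scale should put each event in exactly one category. Here any single alternative is enough for its row, the alternatives in the two rows are not opposites of each other, and no precedence is stated.

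The study's setting produces the conflicting cases. Visits fall 24 and 30 months after the end of the course, so a listed ocular symptom may arise with no temporal link to that course. Further OXERVATE is allowed in follow-up, so an event may also occur during exposure and have another established cause.

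Long-term safety is one of the primary objectives. The related/unrelated call decides whether an event is an adverse drug reaction and where it falls in the relatedness table. With four sites, no comparator and at most 37 patients, differences in how investigators read the table would show directly in that split.

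**Working it through.** The documents give no figure for this point, so there is none to reproduce. The check is logical, with one calculation for scale.

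**Step 1. Write the rows as rules.** Take four yes/no facts from Section 9.3.2: K, known to occur; R, reasonable possibility; T, temporal relationship; A, alternate etiology established.

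- Related = K or R or T
- Unrelated = (not R) or (not T) or A

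**Step 2. Count the 2 × 2 × 2 × 2 = 16 combinations.**

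- Related fails only when K, R and T are all absent. A is free, giving 2 combinations that are Unrelated only.
- Unrelated fails only when R and T are present and A is absent. K is free, giving 2 combinations that are Related only.
- Neither row fits: none, because this would need R both absent and present.
- Both rows fit: 16 − 2 − 2 = **12**.

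**Step 3. Look at late events (T absent).** All 8 combinations are Unrelated, and 6 of them are also Related. If the event is also not known to occur (K absent), 2 of 4 still meet both rows, through R.

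**Step 4. Test the count against a stricter reading.** Someone may hold that R is not a free fact, and that a reasonable possibility exists exactly when timing fits and no other cause is established (R = T and not A). This leaves 8 combinations of K, T and A. Both rows are met when K is present and T absent (2) and when T and A are both present (2), so 4 of 8 still overlap. Those four are the two situations in Step 5.

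**Step 5. Apply the rules to two events.**

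| Event | Why Related | Why Unrelated |
|---|---|---|
| Eye pain first arising at Month 24, no OXERVATE since the course | Known to occur (Appendix 3) | No temporal relationship |
| Event during commercial OXERVATE in follow-up, other cause established | Temporal relationship | Alternate etiology |

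**Step 6. Look for a tie-break.** The closing sentence of the table defines reasonable possibility, so it qualifies only the second Related alternative. It does not restrict the other two. Section 9.1 weighs the same facts but hands the decision to 9.3.2, where each decides alone. No tie-break is given.

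**Step 7. Scale of one changed call.** Because the SAP counts a patient at the closest relationship, one event recorded as Related can move that patient. Exact (Clopper-Pearson) 95% limits for x of n are the 2.5% quantile of Beta(x, n − x + 1) and the 97.5% quantile of Beta(x + 1, n − x). The protocol maximum is n = 37; 25 and 15 are assumptions. The SAP does not say that it will give intervals for adverse events.

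| n | 0 patients with a related event | 1 patient |
|---|---|---|
| 37 | 0% (0 to 9.5) | 2.7% (0.1 to 14.2) |
| 25 | 0% (0 to 13.7) | 4.0% (0.1 to 20.4) |
| 15 | 0% (0 to 21.8) | 6.7% (0.2 to 31.9) |

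**The case against.** **Section 9.1 already supplies the logic.** It calls for judgment on all factors, and it names both situations in Step 5 as arguments against causality: no plausible time to onset, and a more likely alternative explanation. This has force. It makes the problem a drafting defect rather than missing guidance, and many investigators would reach a sensible answer. It does not remove the conflict, because 9.1 sends the classification back to a table in which one factor is enough.

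**The reach into reporting is small.** This stands. Section 9.4.1 requires every serious event to be reported regardless of presumed causality, so none is hidden from the sponsor. Under Section 9.1 a SUSAR must be unexpected, and the listed symptoms ordinarily are not.

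**Little planned output depends on it.** The safety endpoints in Protocol 8.1.3 are adverse events and two eye examinations, not related events. Table 14.3.1.4 is the only listed table whose title splits by relatedness, and no table of drug reactions or SUSARs is planned. That table also relies on the SAP's five-level scale, which the protocol does not collect. How far the 9.3.2 wording drives the table cannot be settled until the two scales are reconciled. This stands too, and the fix must cover it.

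**A conflict with Section 9.4.3 might be inferred.** There the sponsor reports an event to the FDA as a suspected adverse reaction "only if there is evidence to suggest a causal relationship between the drug and the AE". That sentence governs what the sponsor reports. An inclusive investigator classification can coexist with a narrower reporting test, so the documents do not show a contradiction.

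**Conclusion.** The point holds. The two rows are not mutually exclusive, and investigators who follow the table can record opposite answers for the same event. This affects adverse drug reaction status and the relatedness split in Table 14.3.1.4. For SUSARs the effect is limited to serious events that are unlisted or exceed their listed severity or specificity.

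The 12 of 16 is a count of logical cases. How many events are affected is unknown, because the documents give no follow-up event counts. The SAE form and eCRF instructions are also not among them and might restate or resolve the wording.

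Two stronger readings are tempting and unsupported.

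- A reader might infer that the related share of late listed-type events can run from 0% to 100%. That ignores the judgment required by Section 9.1. It also ignores that the table sets no time window and that OXERVATE used in follow-up can give such events a temporal link.
- A reader might take the 33 + 20 = 53 probable or possible events in DEFENDO as a guide to size. That study included the 8-week treatment period and graded events as probable or possible, so it does not predict related events in this follow-up.

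The conclusion assumes that or in each row has its ordinary meaning and that 9.3.2 is the operative rule, as 9.1 says. It is a correctable wording defect in a descriptive study, worth fixing because relatedness feeds a primary objective.

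**What to change.** 1. In Protocol 9.3.2, make the categories complementary using the protocol's own test. Related: a reasonable possibility, meaning evidence to suggest that the Medicinal Product caused the event. Unrelated: no such reasonable possibility.
2. Move known occurrence, temporal relationship and alternate etiology out of the table, and refer to the Section 9.1 factors, to be weighed together.
3. Replace the stray Study Product in the Related row with Medicinal Product.
4. Reconcile the five-level mapping in SAP Section 6.1 with the protocol's binary scale, so that Table 14.3.1.4 is built from what is collected.
5. Carry the same wording into the SAE form and eCRF instructions.
6. Before database lock, have investigators re-check already classified events once, with documentation, and keep the value recorded at the time beside the re-checked one.

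**Cost.** No new data are needed. The change is a wording amendment, which under Protocol 13.4 needs IRB/IEC approval and a signed page from each site's principal investigator, plus a SAP revision. The re-check takes some site time. It is also made in an open-label study with outcomes known and can introduce bias of its own, which is why both values should be kept and any difference reported.
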